11.1 Evaluation of Plasma Drug Concentration

Analysis groups other than the placebo group will be used. Analysis items are shown below.

Plasma drug concentration: Plasma MR13A9 (unchanged drug) concentration

11.1.1 Plasma drug concentration

Summary statistics, geometric mean, and geometric CV will be presented. Geometric means and individual values will be illustrated by dose group.

Assessment time points: Week 1 (before the first dialysis of the week, 5 minutes after

administration, before the second dialysis of the week),

Week 2 (before the first dialysis of the week),

Week 4 (before the first dialysis of the week, 5 minutes after administration, and before the second dialysis of the week),

Week 7 (before the first dialysis of the week, 5 minutes after administration, 1 hour after administration, and before the second

dialysis of the week),

Week 8 (before the first dialysis of the week)

11.1.2 Plasma drug concentration profile

For Week 1 (before the first dialysis of the week, 5 minutes after administration, and before the second dialysis of the week), Week 4 (before the first dialysis of the week, 5 minutes after administration, and before the second dialysis of the week) and Week 7 (before the first dialysis of the week, 5 minutes after administration, and before the second dialysis of the week), the mean values at each time point will be graphically presented by superimposing the dose group.

For Week 1 (before the first dialysis of the week, before the second dialysis of the week), Week 2 (before the first dialysis of the week), Week 4 (before the first dialysis of the week, before the second dialysis of the week), Week 7 (before the first dialysis of the week, before the second dialysis of the week) and Week 8 (before the first dialysis of the week), the mean and standard deviation at each time point will be graphically presented by superimposing the dose group.

For the data at 5 minutes after administration at Weeks 1, 4, and 7, the mean and standard deviation at each time point will be graphically presented by superimposing the dose group.

11.1.3 Plasma drug concentration (Week 7)

For subjects with data obtained at least 1 hour after administration at Week 7, the time course of the measured value in each subject relative to the time (unit: hour) after administration of the study drug on dialysis at Week 7 (before the first dialysis of the week, 5 minutes after administration, at least 1 hour after administration, and before the second dialysis of the week) is presented.

Protocol No. MR13A9-4

Version: 1.0

11.1.4 Plasma drug concentration (dry weight category)

Summary statistics, geometric means, and geometric CVs are presented for the following dry weight categories. Geometric means and individual values will be presented graphically for each dose group for the following dry weight categories. The dry weight category is based on the dry weight at the assessment time points.

Dry weight category: $< 45 \text{ kg}, \ge 45 \text{ and} < 65 \text{ kg}, \ge 65 \text{ and} < 85 \text{ kg}, \ge 85 \text{ kg}$

Assessment time points: Week 1 (before the first dialysis of the week, 5 minutes after

administration),

Week 4 (before the first dialysis of the week, 5 minutes after

administration),

Week 7 (before the first dialysis of the week, 5 minutes after

administration),

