7.2.2 Treatment period

In addition to the use of restricted concomitant medications (e.g., anti-itch drugs) used at the start of the screening period, the study drug will be injected into the venous line of the dialysis circuit at the end of each dialysis session for 8 weeks (3 times weekly, 24 times in total). The injected volume of the study drug will be determined based on the subject's dry weight on the day of dosing according to Table 7.2.2-1. If any dialysis circuit trouble precludes injection through the dialysis circuit, it will be permissible to administer the study drug as an intravenous injection. If a fourth dialysis session is extraordinarily required within the week, the study drug will be administered (up to 4 times weekly). If only the extracorporeal ultrafiltration method is used, the study drug will not be administered. Details are stipulated in a separate procedure.

Table 7.2.2-1 Doses

			MR13A	9 dose	
Dry weight	Injected volume	0.25 μg/kg	0.5 μg/kg	1.0 μg/kg	Placebo
		group	group	group	group
< 45.0 kg	0.35 mL	8.75 μg	17.5 μg	35.0 μg	0 μg
\geq 45.0 kg, $<$ 65.0 kg	0.50 mL	12.50 μg	25.0 μg	50.0 μg	0 μg
\geq 65.0 kg, $<$ 85.0 kg	0.70 mL	17.50 μg	35.0 μg	70.0 μg	0 μg
≥ 85.0 kg	0.85 mL	21.25 μg	42.5 μg	85.0 μg	0 μg

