9.2 Treatment Compliance

The principal investigator or subinvestigator will record compliance with study treatment (day of dosing, time of dosing, route of dosing, dry weight on the day of dosing, drug number, and injected volume) in the case report form.

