10.3 At Week -1

- Review of the symptom diary
- Confirmation of adverse events, concomitant medications, and concomitant therapies
- Examination of specific signs and symptoms

• Confirmation of the implementation status of hemodialysis

10.4 At Week 0

- Review of the symptom diary
- Confirmation of adverse events, concomitant medications, and concomitant therapies
- Examination of specific signs and symptoms
- Confirmation of the implementation status of hemodialysis
- Skindex-16
- 5-D itch scale
- Body weight (before dialysis)
- 12-lead ECG
- Vital signs
- Laboratory tests (hematology, blood biochemistry, endocrinology)
- Confirmation of eligibility and subject registration
- Confirmation of the compliance with study treatment

10.5 At Week 1

- Review of the symptom diary
- Confirmation of adverse events, concomitant medications, and concomitant therapies
- Examination of specific signs and symptoms
- Confirmation of the implementation status of hemodialysis
- Vital signs
- Laboratory tests (hematology, blood biochemistry, endocrinology)
- Confirmation of the compliance with study treatment
- Pharmacokinetics (before the first dialysis and at 5 minutes after administration of the week, before the second dialysis)

10.6 At Week 2

- Review of the symptom diary
- Confirmation of adverse events, concomitant medications, and concomitant therapies
- Examination of specific signs and symptoms
- Confirmation of the implementation status of hemodialysis
- Vital signs
- Laboratory tests (hematology, blood biochemistry, endocrinology)
- Confirmation of the compliance with study treatment
- Pharmacokinetics (before the first dialysis of the week)

10.7 At Week 3

- Review of the symptom diary
- Confirmation of adverse events, concomitant medications, and concomitant therapies
- Examination of specific signs and symptoms
- Confirmation of the implementation status of hemodialysis

10.8 At Week 4

- Review of the symptom diary
- Confirmation of adverse events, concomitant medications, and concomitant therapies
- Examination of specific signs and symptoms
- Confirmation of the implementation status of hemodialysis
- Skindex-16
- 5-D itch scale
- Vital signs
- Laboratory tests (hematology, blood biochemistry, endocrinology)
- Confirmation of the compliance with study treatment
- Pharmacokinetics (before the first dialysis and at 5 minutes after administration of the week, before the second dialysis)

10.9 At Weeks 5 and 6

- Review of the symptom diary

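### SAP 11.1.4 bands the Week 1, 4 and 7 pre-dialysis concentrations by sampling-day dry weight, so a subject whose band changed since the last dose appears under a volume that was not given

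*SAP*

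**What the plan says.** SAP 11.1.4 presents summary statistics, geometric means and geometric CVs, with plots of geometric means and individual values, by dose group within four dry-weight categories: below 45, 45 to below 65, 65 to below 85, and 85 kg or more. Six time points are listed: at each of Weeks 1, 4 and 7, a sample before the week's first session and a sample 5 minutes after dosing (for example "Week 4 (before the first dialysis of the week, 5 minutes after" administration). A single classification rule applies to all six: "The dry weight category is based on the dry weight at the assessment time points".

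The Protocol fixes the order of weight, dose and sample. Section 7.2.2 says "The injected volume of the study drug will be determined based on the subject's dry weight on the day of dosing", and that "the study drug will be injected into the venous line of the dialysis circuit at the end of each dialysis session". The cut points in its Table 7.2.2-1 are the ones SAP 11.1.4 uses. The study schedule places the week's first session on Monday or Tuesday and the last on Friday or Saturday, with dosing from Week 0.

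Protocol 9.2 has the case report form record, for each dose, the day, time and route of dosing, followed by "dry weight on the day of dosing, drug number, and injected volume". SAP 9.5 tabulates subjects whose volume rose, fell, or did both during treatment. Neither document gives a separate rule in 11.1.4 for pre-dialysis samples, or for a subject whose band changed between dose and sample.

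**The concern.** For the 5-minute sample, the weight that assigns the category is also the weight that set the dose just injected, so category and dose agree. For the pre-dialysis sample they need not. The drug being measured was given at an earlier session, at a volume set by that session's dry weight, whereas the category uses a weight that governs an injection still to come. If the weight has crossed a cut point in between, the concentration is listed under a band whose fixed volume the subject did not receive.

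This matters because the categories are the dosing bands. Protocol 7.2.4 says the bands were chosen with ease of preparation in mind, so a natural use of SAP 11.1.4 is to see whether fixed volumes give similar exposure across body size. It is the only planned concentration summary by weight band. At the cut points, where the volume jumps, a cell could contain a level produced by the neighbouring band's volume.

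**Working it through.** **1. The dose table.** Dose = injected volume × vial concentration (Protocol 6.1.1 and Table 7.2.2-1), with concentrations of 25, 50 and 100 µg/mL.
- 0.25 µg/kg group: 0.35, 0.50, 0.70, 0.85 mL × 25 = 8.75, 12.50, 17.50, 21.25 µg.
- 0.5 µg/kg group: the same volumes × 50 = 17.5, 25.0, 35.0, 42.5 µg.
- 1.0 µg/kg group: the same volumes × 100 = 35.0, 50.0, 70.0, 85.0 µg.

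All 12 active doses are reproduced exactly.

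**2. Does the pre-dialysis level come from the last dose?** Protocol 1.3.2.1 gives a half-life of 34.1 to 49.3 h in Japanese hemodialysis patients and, from a non-Japanese study, an average fall of 75% to 80% over dialysis. In a one-compartment approximation with doses 48 h apart, each earlier dose contributes a fraction f = (1 − removal) × 2^(−48/half-life) of the one after it. Over the week's three doses, the last dose's share is 1/(1 + f + f²).
- Removal 75%, half-life 49.3 h: f = 0.25 × 0.509 = 0.127; share = 1/1.143 = 0.87.
- Removal 80%, half-life 34.1 h: f = 0.20 × 0.377 = 0.075; share = 1/1.081 = 0.925.

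So roughly 87% to 93% of the level comes from the preceding session's dose. Three doses are given at Week 0, so this covers the Week 1 sample too.

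**3. Who is affected?** Only a subject who crosses a cut point between the last dose and the first session of Week 1, 4 or 7. With all 24 doses given there are 23 between-dose intervals, and 3 of them matter. A subject who crosses in any other interval has been dosed in the new band before the next of these samples.

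**4. Size of the mismatch.** Ratios of adjacent volumes: 0.50/0.35 = 1.43 at 45 kg; 0.70/0.50 = 1.40 at 65 kg; 0.85/0.70 = 1.21 at 85 kg.

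**5. Effect of one misplaced subject on a geometric mean.** The shift is r^(1/n) − 1, where r is the volume given divided by the volume of the assigned band, and n is the cell size including that subject. The documents give no weight distribution. Assuming N(58, 12) kg and 60 per group, expected cell sizes are 8.4, 34.9, 16.1 and 0.7.

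| Assigned cell | Crossing | r | n | Shift |
|---|---|---|---|---|
| <45 kg | down at 45 | 0.50/0.35 | 8 | +4.6% |
| 45 to <65 kg | up at 45 | 0.35/0.50 | 35 | −1.0% |
| 45 to <65 kg | down at 65 | 0.70/0.50 | 35 | +1.0% |
| 65 to <85 kg | up at 65 | 0.50/0.70 | 16 | −2.1% |
| 65 to <85 kg | down at 85 | 0.85/0.70 | 16 | +1.2% |
| ≥85 kg | up at 85 | 0.70/0.85 | 2 (illustrative) | −9.3% (a factor of 1.10) |

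Range over other cell sizes, taking the largest step (1.43): 7.4% for n = 5, 3.6% for n = 10, 2.4% for n = 15, 1.2% for n = 30.

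These are upper bounds, because they let the misplaced value differ from its cell by the full volume step. If concentration follows dose per kg, a 45 kg subject in the 1.0 µg/kg group given 50 µg (50/45 = 1.11 µg/kg), placed in a <45 kg cell averaging an assumed 40 kg (35/40 = 0.875 µg/kg), differs by 1.11/0.875 = 1.27. The shift in a cell of 8 is then 1.27^(1/8) − 1 = 3.0%.

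**The case against.** The SAP says dry-weight category, not dose band, and it defines the category. A subject at 45.2 kg on the sampling day belongs in the 45 to <65 kg category, so as a label of body size at sampling nothing is wrong. That stands. The mismatch arises only when the category is read as the band of the dose behind the level, a purpose inferred from the shared cut points.

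The analysis has no test, model or decision attached, and Protocol 13.7.1 does not ask for a breakdown by weight. The 5-minute half of the same table matches dose to category, individual values are plotted, and SAP 9.6 summarises actual dose per dry weight. So the affected cells are not the only evidence on the bands. That stands too.

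No crossing rate is given. SAP 9.5 shows that volume changes are foreseen, not that they fall in the three relevant intervals.

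A single sampling-day rule also keeps a subject's two same-day samples in one category. That is a real advantage, and it is lost for band-changers under the fix.

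What the objection does not remove is the timing: no other section reconciles the category of a pre-dialysis level with the dose that produced it.

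**Conclusion.** The point holds in a narrow form and is minor. Three of the six time points in SAP 11.1.4 use a weight recorded after the dose that mainly produced the level, and a subject whose band changed in that gap is shown under a volume not given. The number of such subjects cannot be worked out from the documents and may be zero. If there is one, the shift in a cell's geometric mean is at most about 5% in the lowest band, 1% in the 45 to <65 kg band, 2% in the 65 to <85 kg band, and about 10% in a top-band cell of 2.

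These sizes rest on the assumed weight distribution, on all 60 subjects per group contributing, and on the full volume step. SAP 6.2 drops values below quantification from geometric means, so actual cells could be smaller.

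Three stronger readings are not supported:
- A reader might infer that anyone who changes band during treatment is misplaced. Only a change between the last dose and a listed sampling session counts.
- A reader might pair the 1.43 step with a cell of 2 and get about 20%. That step exists only at 45 kg, between cells of about 8 and 35 under the same assumption.
- A reader might suppose that efficacy or power is touched. The primary analysis, sample size and significance level do not use these data.

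**What to change.** Replace the classification sentence in SAP 11.1.4 with:

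> For 5-minute samples the category is based on the dry weight on the day of sampling; for pre-dialysis samples it is based on the dry weight recorded at the most recent dose before the sample.

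Use the recorded dry weight and do not treat the injected volume as equivalent, since the two part company if a volume departs from the table. List or flag subjects whose band differs between that dose and the sampling session, because their two same-day samples will fall in different categories.

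The cost is one sentence and one merge with the dosing records already collected under Protocol 9.2. No new data are needed, and the 5-minute results do not change. The new rule also gives a category when no dose is given on a sampling day, a case in which Protocol 9.2 calls for no dry weight that day. It changes only an analysis category and no dosing rule.

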11.1.5 Time elapsed after administration (Week 7, at least 1 hour after administration)

The time elapsed from the study drug administration to blood sampling for plasma drug concentration at the time point of assessment is regarded as the time elapsed after the last administration (unit: hour).

Summary statistics will be presented only for data obtained at least 1 hour after administration at Week 7.

12. Safety

12.1 Adverse Events and Adverse Drug Reactions

Unless otherwise specified, the following events will be tabulated.

- Events occurring between the start of study treatment and the end of the follow-up period
- Events occurring between the start of study treatment and the end of the treatment period
- Adverse events of special interest occurring between the start of study treatment and the end of the follow-up period
- Adverse events of special interest occurring between the start of study treatment and the end of the treatment period

12.1.1 Incidence of adverse events and adverse drug reactions

The number of events, the number of subjects experiencing events, the incidence of events and its two-sided 95% confidence interval will be presented. Fisher's exact test will be used for comparisons between the placebo group and each of the MR13A9 0.25, 0.5, and 1.0 μ g/kg groups. The difference in the incidence between the placebo group and the MR13A9 0.25, 0.5, and 1.0 μ g/kg groups and its two-sided 95% confidence interval will be presented.

12.1.2 Incidences of adverse events and adverse drug reactions (serious adverse events, adverse events leading to discontinuation of treatment period, and adverse events of special interest)

For adverse events occurring between the start of study treatment to the end of the follow-up

Protocol No. MR13A9-4 Version: 1.0

period, and adverse events between the start of treatment with the study drug to the end of the treatment period, the number of events, the number of subjects experiencing events, and the incidence of all events, adverse events leading to death, serious adverse events excluding death, events leading to interruption, events leading to discontinuation of the treatment period, and adverse events of special interest will be presented.

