2.2 Development Phase

Phase II

3. Study Objectives

To determine the dose-response relationship for the efficacy, safety, and pharmacokinetics of MR13A9 0.25, 0.5, or 1.0 μ g/kg administered to previously treated hemodialysis patients with pruritus for 8 weeks in a placebo-controlled, double-blind design.

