3.3.2 Rationale for the pharmacokinetic endpoint

This endpoint has been established to determine the pharmacokinetic dose-response relationship in Japanese hemodialysis patients with pruritus.

4. Study Population

This study will enroll previously treated hemodialysis patients with pruritus who meet all of the inclusion criteria and none of the exclusion criteria below.

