7.6 Sample Size

7.6.1 Sample size

This study will enroll 60 subjects for each MR13A9 dose group and the placebo group, 240 subjects in total.

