All statistical tests will be performed using a two-sided significance level of 5%; however, a two-sided significance level of 15% will be used for the analysis of between-group imbalance. Summary statistics will be presented as the number of subjects, mean, standard deviation, minimum, median, maximum, and quartile. Unless otherwise specified, data will be tabulated by group and by time point. Week 0 will be the baseline.

SAS System Release 9.4 for Windows (SAS Institute Inc.) will be used to conduct the analysis.

4. Analysis Sets

The analysis sets are defined as follows. When the full analysis set (FAS) and the per protocol set (PPS) are used as analysis sets, analyses will be performed based on the treatment group to which each subject has been allocated. When the safety set (SS) and the pharmacokinetic analysis set (PKS) are used as analysis sets, analyses will be performed based on the treatment group in which each subject has been actually treated.

- FAS: Population of subjects, excluding the following subjects: subjects with GCP violations, untreated subjects, discontinued subjects before entry to the treatment period, some of the ineligible subjects, and subjects with no available mean NRS score at baseline (Week 0)
- PPS: Population of subjects, excluding the following subjects from the FAS: ineligible subjects, discontinued subjects, deviators, and subjects with broken emergency key codes, as the subjects to be excluded from the PPS

Statistical Analysis Plan	Protocol No. MR13A9-4
	Version: 1.0

- SS: Population of subjects, excluding the following subjects: subjects with GCP violations, untreated subjects, and discontinued subjects before entry to the treatment period
- PKS: Population of subjects, excluding the following subjects from the SS: subjects with no available plasma drug concentration data

Correspondence of the analysis items and the analysis sets is shown in Table 4-1.

Table 4-1 Analysis Items and Analysis Sets

Endpoints	Analysis items	Analysis sets
Demographic and other baseline	Subject demographics	FAS, PPS, SS, PKS
characteristics	Other	SS
Treatment compliance	All items	FAS, SS
Efficacy	Primary variable (primary analysis)	FAS (primary analysis set), PPS
	Other	FAS
Pharmacokinetics	All items	PKS
Safety	All items	SS

5. Analysis Groups

- MR13A9 0.25 μg/kg group: Subjects allocated to or treated with MR13A9 0.25 μg/kg
- MR13A9 0.5 μg/kg group: Subjects allocated to or treated with MR13A9 0.5 μg/kg

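### The objective covers dose-response for safety and pharmacokinetics, but only efficacy gets a dose-response analysis; safety and PK rest on by-dose description

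*SAP*

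**What the plan says.** Protocol section 3 gives one objective: "To determine the dose-response relationship for the efficacy, safety, and pharmacokinetics" of MR13A9 at three doses over 8 weeks. Protocol 3.3.2 repeats it as the reason for the PK endpoint: "to determine the pharmacokinetic dose-response relationship in Japanese hemodialysis patients with pruritus". Protocol 7.2.4 adds that efficacy and safety profiles together are to inform the recommended doses.

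The planned analyses are:

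- **Efficacy** (SAP 10.1.1.1.1): contrasts across placebo and the three doses within the MMRM, with a p-value for each pattern.
- **Adverse events** (SAP 12.1.1; protocol 13.6.1 agrees): event counts; incidence with a 95% interval in each group; the difference from placebo with a 95% interval for each dose; and "Fisher's exact test will be used for comparisons between the placebo group and each of the MR13A9" dose groups.
- **PK** (SAP 11.1.1 to 11.1.5): "Summary statistics, geometric mean, and geometric CV will be presented", with plots by dose group, doses superimposed over time, and a repeat by dry-weight band.

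Neither document plans a trend test, contrast or dose model for safety, or a dose-proportionality analysis for PK. SAP 6.5.2 and 6.5.3 treat everything except the primary variable as reference, without multiplicity adjustment.

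**The concern.** A dose-response question asks how the outcome changes as dose rises. Three separate comparisons with placebo do not use the order of the doses, and each uses half of the 240 subjects. Geometric means by nominal group do not say whether concentration rises in proportion to dose.

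Nominal group is also a coarse label for dose. Injected volume is fixed within a dry-weight band, so actual dose per kg varies within each group, and no planned PK analysis relates concentration to the dose per kg each subject received.

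At stake is whether the report can give a quantified answer to two of the three parts of its own objective, which matters when a dose is being chosen.

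**Working it through.** **1. The plan's own figure.** The documents give a dose-response power only for efficacy. Inputs from protocol 7.6.2: differences 0, -0.6, -1.3, -1.3; SD 2.5; contrast (3, 1, -2, -2); 60 per group (protocol 7.6.1).

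- Contrast value: 1 × (-0.6) - 2 × (-1.3) - 2 × (-1.3) = 4.6
- Standard error: 2.5 × √(18/60) = 1.369
- Noncentrality: 4.6/1.369 = 3.36
- Power, noncentral t with 4 × 59 = 236 df, two-sided 5%: 91.7%, as stated

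The Week 2 figure of 76.4% also reproduces. No power is stated for a safety or PK dose-response.

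**2. PK: spread of actual dose.** From the dose table in protocol 7.2.2 and the 24 kg dry-weight floor in protocol 4.2.1, the 1.0 µg/kg group receives per kg:

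- at 24 kg: 35/24 = 1.46
- just under 45 kg: 35/45 = 0.78; at 45 kg: 50/45 = 1.11
- just under 65 kg: 50/65 = 0.77; at 65 kg: 70/65 = 1.08
- just under 85 kg: 70/85 = 0.82; at 85 kg: 85/85 = 1.00

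The permitted range is therefore about 0.77 to 1.46 µg/kg (lower only above 85/0.769 = 110.5 kg). The other groups scale the same way: the top of the 0.5 group is 17.5/24 = 0.73, close to the bottom of the 1.0 group.

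**3. PK: is proportionality already settled?** Study MR13A9-2 (protocol 1.3.2.1) gives means at 0.5 and 1 µg/kg. The implied exponent is log2 of their ratio:

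- Cmax, first dose: log2(8.95/4.38) = 1.03
- Cmax, third dose: log2(8.69/5.38) = 0.69
- AUC to infinity, first dose: log2(240.05/97.38) = 1.30
- AUC to infinity, third dose: log2(316.85/151.34) = 1.07

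Proportionality means 1.0. The values scatter around it; the protocol gives no group sizes for that study, so no intervals can be attached.

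**4. PK: precision of a slope here.** The Cmax CVs from the same study are 1.31/4.38 = 30%, 2.24/8.95 = 25%, 1.84/5.38 = 34% and 2.45/8.69 = 28%. Assume lognormal values, this CV at 5 minutes, one value per subject and 60 subjects at each of three doses (nominal spacing ln 2).

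- Log-scale SD = √ln(1 + CV²): 0.246 to 0.331
- Sxx = 60 × 2 × (ln 2)² = 57.65
- SE = SD/√57.65: 0.032 to 0.044
- 95% half-width = 1.96 × SE: 0.06 to 0.09

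**5. Safety: power by simulation.** 60 evaluable per arm, two-sided 5%. The fair comparator for one trend test is at least one of the three planned Fisher tests. Rates are for placebo/0.25/0.5/1.0. The first three rows are assumed; the last two come from study MR13A9-3 (protocol 1.3.2.2), with dizziness on placebo, which is not listed there, assumed to be 0.

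| Rates (%) | Trend, rank scores | Trend, dose scores | At least one Fisher | Fisher, 1.0 v placebo |
|---|---|---|---|---|
| 10/15/20/25 | 63% | 61% | 56% | 49-50% |
| 25/30/35/40 | 46% | 44-45% | 41% | 34% |
| 5/8/12/18 | 69% | 68% | 55-56% | 51% |
| Dizziness 0/4.8/9.5/10.5 | 80-81% | 69-70% | 82% | 61% |
| Reactions 23.8/33.3/61.9/47.4 | 95% | 85% | 99% | 71% |

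A range means that repeated runs differed in the last digit.

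**6. Safety: error under no effect.** The trend test rejects in about 5% of trials. At least one Fisher test is positive in about 3% at a 5% event rate and about 6-8% at 10-30%.

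**The case against.** The strongest reply is that the dose-response is already estimated. SAP 12.1.1 gives incidence and risk difference with intervals at every dose, which is a dose-response with dose as a category. The PK plots show the doses together, and SAP 11.1.4 repeats the summaries by weight band. Descriptive safety and PK are common in phase II, and these items are declared reference only. All of this stands. A reader might infer that neither relationship is estimated at all; the documents do not support that.

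A reader might also infer that the Fisher tests are simply the less sensitive choice because earlier reaction rates rise with dose. They do not rise steadily over this trial's doses. In MR13A9-3 reactions were higher at 0.5 than at 1.0. In CLIN2101 they were 2.2% on placebo and 27.3%, 26.8% and 22.7% at 0.5, 1.0 and 1.5: a step, then flat. Setting the trend test against the single 1.0 comparison (63% v 50%, or 80% v 61% for dizziness) flatters it, because three Fisher tests are planned.

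Finally, SAP 9.6 might seem to supply the actual dose per kg already. It is an average over the treatment period, not the dose at the sampled session.

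What survives is narrower. The objective sets the same task for three domains and only one has a method for it. By-dose tables do not yield a slope or a test of trend.

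**Conclusion.** The mismatch is real and of low priority. No trend test or dose-response model is planned for safety and no dose-proportionality analysis for PK, so those parts of the objective rest on by-dose estimates and description.

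The PK part is the firmer. Actual dose varies widely within nominal groups, the earlier exponents run from 0.69 to 1.30, and this trial could estimate the slope to within about ±0.06 to ±0.09. That precision assumes CVs like those in MR13A9-2 and 60 evaluable subjects per dose.

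The safety part is a modest supplement. Against at least one of three Fisher tests, the rank-score trend test gains about 5 to 14 points for the assumed monotone rises. It has no advantage for the dizziness rates and loses 4 points (rank scores) or 14 points (dose scores) for the earlier overall reaction rates. In the two monotone cases with higher rates, part of the Fisher power comes with an error rate above 5%. The documents give no dropout rate, so all power figures assume 60 evaluable per arm.

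The primary efficacy analysis and its stated power are not affected.

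**What to change.** 1. **SAP 11.1.1:** add a linear regression of log concentration at 5 minutes after administration on log actual dose per kg at that session, with slope and 95% confidence interval, for each of Weeks 1, 4 and 7. Derive the dose from the injected volume, the vial strength and the dry weight on the day of dosing (volume and dry weight are recorded under protocol 9.2), not from the period average in SAP 9.6. Exclude placebo, as SAP 11.1 already does.
2. **SAP 12.1.1:** add, as a supplement, a two-sided Cochran-Armitage trend test across placebo, 0.25, 0.5 and 1.0 for adverse events, adverse drug reactions and adverse events of special interest. Fix the scores in advance, since rank and dose scores can differ by 10 points or more in power. Keep the pairwise differences with intervals, because a trend test can miss a flat or non-monotone response. Give the p-values the same reference status as other safety results.

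The minimum alternative is to reword the objective to say that safety and PK are described by dose.

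The cost of the two additions is a few lines of SAP text and code on data already collected. No change to the sample size, visits or primary analysis is needed.
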